4.5 Toxicity Management

Any patient who receives at least one dose of study drug will be evaluable for toxicity endpoints. Toxicity will be assessed according to CTCAE v 4.03 criteria

4.5.1 Immune-Related Adverse Events

The limited systemic absorption of chemotherapy agents and cytokines (i.e., IFN) when administered intravesically predicts that immune-related adverse events (irAEs) observed in patients receiving intravenous pembrolizumab will be rare. Nevertheless, all measures will be in place for careful monitoring and management should these occur

Table 4-4. Dose Modification and Toxicity Management Guidelines for Immune-related AEs Associated with Pembrolizumab

General instructions:				
Immune-related AEs	Toxicity grade or conditions (CTCAEv4.0)	Action taken to pembrolizumab	irAE management with corticosteroid and/or other therapies	Monitor and follow-up
Pneumonitis	Grade 2	Withhold	
 Administer corticosteroids (initial dose of 1-2 mg/kg prednisone or equivalent) followed by taper 	
 Monitor participants for signs and symptoms of pneumonitis Evaluate participants with suspected pneumonitis with radiographic imaging and initiate corticosteroid treatment Add prophylactic antibiotics for opportunistic infections
	Grade 3 or 4, or recurrent Grade 2	Permanently discontinue		
Diarrhea / Colitis	Grade 2 or 3	Withhold	
 Administer corticosteroids (initial dose of 1-2 mg/kg prednisone or equivalent) followed by taper 	
 Monitor participants for signs and symptoms of enterocolitis (i.e., diarrhea, abdominal pain, blood or mucus in stool with or without fever) and of bowel perforation (i.e., peritoneal signs and ileus). Participants with \geq Grade 2 diarrhea suspecting colitis should consider GI consultation and performing endoscopy to rule out colitis. Participants with diarrhea/colitis should be advised to drink liberal quantities of clear fluids. If sufficient oral fluid intake is not feasible, fluid and
	Grade 4	Permanently discontinue		

NU Study Number: NU 15U06
Merck Study Number: 3475-265

				electrolytes should be substituted via IV infusion.
AST / ALT elevation or Increased bilirubin	Grade 2	Withhold	
 Administer corticosteroids (initial dose of 0.5- 1 mg/kg prednisone or equivalent) followed by taper 	
 Monitor with liver function tests (consider weekly or more frequently until liver enzyme value returned to baseline or is stable)
	Grade 3 or 4	Permanently discontinue	
 Administer corticosteroids (initial dose of 1-2 mg/kg prednisone or equivalent) followed by taper 	
Type 1 diabetes mellitus (T1DM) or Hyperglycemia	Newly onset T1DM or Grade 3 or 4 hyperglycemia associated with evidence of β -cell failure	Withhold	
 Initiate insulin replacement therapy for participants with T1DM Administer anti-hyperglycemic in participants with hyperglycemia 	
 Monitor participants for hyperglycemia or other signs and symptoms of diabetes.
Hypophysitis	Grade 2	Withhold	
 Administer corticosteroids and initiate hormonal replacements as clinically indicated. 	
 Monitor for signs and symptoms of hypophysitis (including hypopituitarism and adrenal insufficiency)
	Grade 3 or 4	Withhold or permanently discontinue ¹		
Hyperthyroidism	Grade 2	Continue	
 Treat with non-selective beta-blockers (e.g., propranolol) or thionamides as appropriate 	
 Monitor for signs and symptoms of thyroid disorders.
	Grade 3 or 4	Withhold or permanently discontinue ¹		
Hypothyroidism	Grade 2-4	Continue	
 Initiate thyroid replacement hormones (e.g., levothyroxine or liothyroinine) per standard of care 	
 Monitor for signs and symptoms of thyroid disorders.
Nephritis and Renal dysfunction	Grade 2	Withhold	
 Administer corticosteroids (prednisone 1-2 mg/kg or equivalent) followed by taper. 	
 Monitor changes of renal function
	Grade 3 or 4	Permanently discontinue		
Myocarditis	Grade 1 or 2	Withhold	
 Based on severity of AE administer corticosteroids 	
 Ensure adequate evaluation to confirm etiology and/or exclude other causes
	Grade 3 or 4	Permanently discontinue		
All other immune-related AEs	Intolerable/ persistent Grade 2	Withhold	
 Based on type and severity of AE administer corticosteroids 	
 Ensure adequate evaluation to confirm etiology and/or exclude other causes
	Grade 3	Withhold or discontinue based on the type of event. Events that		

		require discontinuation include and not limited to: Gullain-Barre Syndrome, encephalitis		
	Grade 4 or recurrent Grade 3	Permanently discontinue		

1. Withhold or permanently discontinue pembrolizumab is at the discretion of the investigator or treating physician.
 
NOTE: For participants with Grade 3 or 4 immune-related endocrinopathy where withhold of pembrolizumab is required, pembrolizumab may be resumed when AE resolves to ≤ Grade 2 and is controlled with hormonal replacement therapy or achieved metabolic control (in case of T1DM).
				

4.5.2 Management of Specific Adverse Events

In addition to the table above, subjects should receive appropriate supportive care measures as deemed necessary by the treating investigator including but not limited to the items outlined below:

- Anti-infectives: Subjects with a documented infectious complication should receive oral or IV antibiotics or other anti-infective agents as considered appropriate by the treating investigator for a given infectious condition, according to standard institutional practice. Please refer to section 4.4 for guidance regarding delay of treatment up to 2 weeks (14 days) for local, treatment-related, bladder and urinary tract infections.
- Management of Infusion Reactions: NOTE: intravenous infusion is no the route of administration that will be employed in this protocol. The risk of these reactions is relevant with intravenous administration of pembrolizumab and it is not expected to be clinically significant with intravesical administration. However, all measures will be in place for careful monitoring and management should these occur. Acute infusion reactions (which can include cytokine release syndrome, angioedema, or anaphylaxis) are different from allergic/hypersensitive reactions, although some of the manifestations are common to both AEs. Signs and symptoms usually develop during or shortly after drug infusion and generally resolve completely within 24 hours of completion of infusion. Signs/symptoms may include: Allergic reaction/hypersensitivity (including drug fever); Arthralgia (joint pain); Bronchospasm; Cough; Dizziness; Dyspnea (shortness of breath); Fatigue (asthenia, lethargy, malaise); Headache; Hypertension; Hypotension; Myalgia (muscle pain); Nausea; Pruritis/itching; Rash/desquamation; Rigors/chills; Sweating (diaphoresis); Tachycardia; Tumor pain (onset or exacerbation of tumor pain due to treatment); Urticaria (hives, welts, wheals); Vomiting.

Table below shows treatment guidelines for subjects who experience an infusion reaction associated with intravenous administration of pembrolizumab. In the event that an infusion-like reaction does occur with intravesical administration of a patient on this study, the guidelines below should be followed.

Table 4-5: Management of Infusion Reactions		
NCI CTCAE Grade	Treatment	Premedication at subsequent dosing
Grade 1 Mild reaction; infusion interruption not indicated; intervention not indicated	Increase monitoring of vital signs as medically indicated until the subject is deemed medically stable in the opinion of the investigator.	None
Grade 2 Requires infusion interruption but responds promptly to symptomatic treatment (e.g., antihistamines, NSAIDS, narcotics, IV fluids); prophylactic medications indicated for < =24 hrs	
Stop Infusion and monitor symptoms.
 
Additional appropriate medical therapy may include but is not limited to:
 
 IV fluids Antihistamines NSAIDS Acetaminophen Narcotics 
Increase monitoring of vital signs as medically indicated until the subject is deemed medically stable in the opinion of the investigator.
 
If symptoms resolve within one hour of stopping drug infusion, the infusion may be restarted at 50% of the original infusion rate (e.g. from 100 mL/hr to 50 mL/hr). Otherwise dosing will be held until symptoms resolve and the subject should be premedicated for the next scheduled dose.
 
Subjects who develop Grade 2 toxicity despite adequate premedication should be permanently discontinued from further trial treatment administration.
	
Subject may be premedicated 1.5h (\pm 30 minutes) prior to infusion of pembrolizumab with:
 
 • Diphenhydramine 50 mg po (or equivalent dose of antihistamine). • Acetaminophen 500-1000 mg po (or equivalent dose of antipyretic).
Grades 3 or 4 Grade 3: Prolonged (i.e., not rapidly responsive to symptomatic medication and/or brief interruption of infusion);	
Stop Infusion.
 
Additional appropriate medical therapy may include but is not limited to:
 
 IV fluids Antihistamines NSAIDS 	No subsequent dosing

recurrence of symptoms following initial improvement; hospitalization indicated for other clinical sequelae (e.g., renal impairment, pulmonary infiltrates)
 
Grade 4: Life-threatening; pressor or ventilatory support indicated
	
Acetaminophen Narcotics Oxygen Pressors Corticosteroids Epinephrine
 
Increase monitoring of vital signs as medically indicated until the subject is deemed medically stable in the opinion of the investigator.
 
Hospitalization may be indicated.
 
Subject is permanently discontinued from further trial treatment administration.
	
Appropriate resuscitation equipment should be available in the room and a physician readily available during the period of drug administration.		
For Further information, please refer to the Common Terminology Criteria for Adverse Events v4.03 (CTCAE) at http://ctep.cancer.gov		

4.5.3 Overview of Guidelines for Managing Suspected Pneumonitis from pembrolizumab

Subjects with symptomatic pneumonitis should immediately stop receiving pembrolizumab and have an evaluation. The evaluation may include bronchoscopy and pulmonary function tests to rule out other causes such as infection. If the subject is determined to have study drug associated pneumonitis, the suggested treatment plan is detailed in the table below.

Table 4-6: Management of Pneumonitis		
Study drug associated pneumonitis	Withhold/Discontinue pembrolizumab?	Supportive Care
Grade 1 (asymptomatic)	No action	Intervention not indicated
Grade 2	Withhold pembrolizumab, may return to treatment if improves to Grade 1 or resolves within 2 weeks	Systemic corticosteroids are indicated. Taper if necessary.
Grade 3 and Grade 4	Discontinue pembrolizumab	Systemic corticosteroids are indicated. The use of infliximab may be indicated as appropriate. Refer to the Event of Clinical Interest and Immune-related Adverse Event Guidance Document for additional recommendations.

For Grade 2 pneumonitis that improves to \leq Grade 1 within 2 weeks, the following rules should apply:

First episode of pneumonitis

- May increase dosing interval by one week in subsequent cycles
- Second episode of pneumonitis – permanently discontinue pembrolizumab if upon rechallenge subject develops pneumonitis \geq Grade 2

4.5.4 Supportive Care Guidelines for Events of Clinical Interest and Immune-related Adverse Events (irAEs)

Events of clinical interest of a potential immunologic etiology (irECIs) may be defined as an adverse event of unknown etiology, associated with drug exposure and is consistent with an immune phenomenon. irAEs may be predicted based on the nature of the pembrolizumab compound, its mechanism of action, and reported experience with immunotherapies that have a similar mechanism of action. Special attention should be paid to AEs that may be suggestive of potential irAEs. An irAE can occur shortly after the first dose or several months after the last dose of treatment.

If an irAE is suspected, efforts should be made to rule out neoplastic, infectious, metabolic, toxin or other etiologic causes prior to labeling an adverse event as an irAE. Information on how to identify and evaluate irAEs has been developed and is included in the Event of Clinical Interest and Immune-Related Adverse Event Guidance Document located in the Administrative Binder. Subjects who develop a Grade 2 or higher irAE should be discussed immediately with the Sponsor.

Recommendations to managing irAEs not detailed elsewhere in the protocol are detailed in the table below.

Table 4-7: Management of irAEs		
irAE	Withhold/Discontinue pembrolizumab	Supportive Care
Grade 1	No action	Provide symptomatic treatment
Grade 2	May withhold pembrolizumab	Consider systemic corticosteroids in addition to appropriate symptomatic treatment
Grade 3 and Grade 4	Withhold pembrolizumab Discontinue if unable to reduce corticosteroid dose to < 10 mg per day prednisone equivalent within 2 weeks of toxicity	Systemic corticosteroids are indicated in addition to appropriate symptomatic treatment. May utilize 1 to 2 mg/kg prednisone or equivalent per day. Steroid taper should be considered once symptoms improve to Grade 1 or less and tapered over at least 4 weeks.

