4.4 Dose Delays/Modifications

Symptoms of local toxicity will be monitored throughout treatment. Treatment will be delayed for up to 2 weeks (14 days) if grade 2 local toxicity (not considered DLT) develops during pre-induction, induction, or maintenance phases. In addition, BCG dose modifications will be managed according to standard of care procedures; specifically, in the case of a grade 2 local bladder toxicity, the dose should be delayed, and BCG may be re-challenged at half the dose (25mg) per the treating physician's discretion within 2 weeks (14 days) of the last administration. Local toxicities related to the treatment with BCG and/or pembrolizumab include bladder spasm, cystitis noninfective, hematuria, urinary frequency, urinary retention, urinary tract pain, urgency. In addition, for grade 2 bladder or urinary tract infection, treatment *may be delayed* up to 2 weeks at the discretion of the treating physician; for grade 3 bladder or urinary tract infection, antibiotics are allowed with a 2 week delay of treatment as long as the infection has been cleared symptomatically. Treatment may resume when the toxicity resolves or improves to grade 1. If toxicity does not resolve to Grade 0-1 within 2 weeks (14 days) after scheduled dose, trial treatment should be discontinued after consultation with the PI and DSMC.

The patients will be allowed to delay treatment during induction or maintenance by up to 2 weeks (14 days) due to scheduling difficulties. When BCG is delayed due to local bladder toxicities, pembrolizumab will be delayed as well. Doses of pembrolizumab will not be reduced due to toxicities. BCG doses may be reduced following standard of care as described above. If the patient needs to undergo a transurethral biopsy or resection during the study, there will be a delay of approximately 4 weeks (per PI discretion) until the next treatment of BCG or pembrolizumab to allow healing of biopsy/resection site.

In addition, pembrolizumab will be withheld for drug-related Grade 4 hematologic toxicities, non-hematological toxicity \geq Grade 3 including laboratory abnormalities, and severe or life-threatening AEs. Delay by up to 2 weeks (14 days) is permitted. Treatment may resume when the toxicity resolves or improves to grade 1. If toxicity does not resolve to Grade 0-1 within 2 weeks (14 days) after the scheduled dose

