administration, trial treatment should be discontinued after consultation with the PI and DSMC. With PI and DSMC agreement, subjects with a laboratory adverse event still at Grade 2 after 2 weeks may continue treatment in the trial only if asymptomatic and controlled.

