4.5.4.2 Other Immune-Mediated Adverse Reactions

The following additional clinically significant, immune-mediated adverse reactions were reported in less than 1% of patients treated with pembrolizumab in KEYNOTE-001, KEYNOTE-002, KEYNOTE-006, and KEYNOTE-010: uveitis, myositis, Guillain-Barré syndrome, and pancreatitis. The following was reported in other clinical studies with pembrolizumab or in post-marketing use: myocarditis.

Cases of these immune-mediated adverse reactions, some of which were severe, have been reported in clinical trials or in post-marketing use.

Solid organ transplant rejection has been reported in the post-marketing setting in patients treated with pembrolizumab. Treatment with pembrolizumab may increase the risk of rejection in solid organ transplant recipients. Consider the benefit of treatment with pembrolizumab versus the risk of possible organ rejection in these patients.

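### For immune-related events without their own row, Table 4-4 permanently stops pembrolizumab at Grade 4 or recurrent Grade 3, while Table 4-7 and Section 4.4 leave re-dosing open if the event improves in time

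*Combined protocol and SAP*

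**What the plan says.** Three places tell the investigator what to do with pembrolizumab after a serious irAE that has no row of its own.

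- **Section 4.5.1, Table 4-4, row for all other irAEs.** At Grade 3 the action is "Withhold or discontinue based on the type of event", with an open list of events that "require discontinuation include and not limited to: Gullain-Barre Syndrome, encephalitis". The trigger for permanent discontinuation is "Grade 4 or recurrent Grade 3", with no condition attached.
- **Section 4.5.4, Table 4-7.** The lead-in reads "Recommendations to managing irAEs not detailed elsewhere in the protocol are detailed in the table below". Grades 3 and 4 share one row: "Withhold pembrolizumab Discontinue if unable to reduce corticosteroid dose to < 10 mg per day prednisone equivalent within 2 weeks of toxicity". The row has no rule for recurrence and no sentence on when to restart. The supportive-care cell says steroids are indicated, allows 1 to 2 mg/kg per day, and asks that a taper over at least 4 weeks be considered once symptoms reach Grade 1 or less.
- **Section 4.4, paragraph on withholding pembrolizumab.** The drug is withheld for drug-related Grade 4 hematologic toxicity, for non-hematologic toxicity of Grade 3 or higher, and for "severe or life-threatening AEs. Delay by up to 2 weeks (14 days) is permitted. Treatment may resume when the toxicity resolves" or falls to Grade 1. If Grade 0-1 is not reached within 14 days after the scheduled dose, treatment should be discontinued after consultation with the PI and DSMC. With their agreement, "subjects with a laboratory adverse event still at Grade 2 after 2 weeks may continue treatment in the trial only if asymptomatic and controlled". The paragraph does not refer to Table 4-4.

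Section 4.5.4 also requires that any irAE of Grade 2 or higher be discussed with the sponsor immediately, and it points to a separate guidance document on irAEs.

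**The concern.** Table 4-4 and Table 4-7 both contain a residual rule for irAEs that are not handled individually, and the two differ at the grades that matter most. One is an unconditional permanent stop. The other is a withhold that becomes a stop only if a steroid target is missed. Section 4.4 then supplies a restart criterion that takes no account of the permanent stop.

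At stake is re-exposure to a checkpoint inhibitor after a life-threatening or repeated severe immune event that the protocol elsewhere treats as the end of treatment. The events are not purely hypothetical. Section 4.5.4.2 says that "additional clinically significant, immune-mediated adverse reactions were reported in less than 1% of patients treated with pembrolizumab" in four named studies, and lists uveitis, myositis, Guillain-Barré syndrome and pancreatitis. Only Guillain-Barré syndrome is named in Table 4-4. The other three fall to its residual row.

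**Working it through.** No plan figure has to be reproduced. The check sets the three rules side by side and follows test cases through them.

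**Case A.** A Grade 4 irAE without its own row, such as pancreatitis, improves to Grade 1 within the 14 days allowed, with prednisone equivalent below 10 mg/day within 2 weeks of the toxicity.

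**Case B.** A second Grade 3 episode of such an irAE runs the same course.

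**Case C.** As A or B, but the toxicity reaches Grade 1 in time while steroids stay at 10 mg/day or more.

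**Case D.** As A or B, but neither the toxicity nor the steroid dose comes down in time.

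| Case | Table 4-4 | Table 4-7 | Section 4.4 |
|---|---|---|---|
| A | Permanent stop | Withhold; stop not triggered | May resume |
| B | Permanent stop | Withhold; stop not triggered | May resume |
| C | Permanent stop | Discontinue | May resume |
| D | Permanent stop | Discontinue | Discontinue after consultation |

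The rules conflict in A and B. In C the two tables agree and only Section 4.4 differs, because it has no steroid limit. In D all three lead to a stop. The divergence is therefore confined to events that improve in time.

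**How often Table 4-7's steroid target could be met.** The documents give no distribution of steroid courses, so this is a bounding calculation under an assumption: a linear taper over 28 days (the 4-week minimum) that starts on the day of the toxicity, which is the earliest possible start.

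- Dose at day 14 = starting dose × (28 − 14)/28 = starting dose × 0.5.
- A day-14 dose below 10 mg requires a starting dose below 10/0.5 = 20 mg/day.
- At 1 mg/kg, that requires a body weight below 20 kg. At 2 mg/kg, it requires a weight below 10 kg.

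Under that taper no adult weighing 20 kg or more meets the target, so Table 4-7 would also end in discontinuation. A lower starting dose or a front-loaded taper could meet it, and both are open because the dose and taper wording is advisory.

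**Effect on the primary result.** Under Table 4-3 a related non-hematologic event of Grade 3 or higher is already a DLT when it occurs in the observation period, apart from the exceptions listed there. Section 4.11 makes a subject evaluable for DLT on the week −2 dose. Whether pembrolizumab is restarted afterwards changes neither the classification nor the denominator.

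**The case against.** The strongest reply is that precedence is already supplied. Table 4-7 limits itself to irAEs not dealt with elsewhere, and Table 4-4's residual row does deal with Grade 4 and recurrent Grade 3, so Table 4-7 yields by its own terms. It would not be left empty: it still covers Grade 1, Grade 2 events that are neither intolerable nor persistent, and the steroid dose and taper. The amendment history in Appendix C points the same way, since Table 4-4's content was updated in Amendment 6, after the last listed change to Section 4.5.4. Section 4.4 can likewise be read as a permissive general rule that gives way to a specific mandatory one. This is also a single-center study in which the PI oversees treatment of every patient, and the guidance document, not available here, may settle the matter.

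Much of this stands, and it is why the point is minor. What remains is that, on this reading, the pembrolizumab action in Table 4-7's Grade 3-4 row governs nothing, yet a weaker stopping rule stays in a safety table. No text states which rule prevails, and the lead-in to Table 4-7 does not reach Section 4.4. Sponsor discussion lowers the risk but does not say which rule should guide that discussion.

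A reader might also infer more than the text supports. Table 4-7 does not merely withhold; it has a conditional stop. Section 4.4 does not allow unconditional resumption; it requires recovery to Grade 0-1 within 14 days after the scheduled dose. The allowance for Grade 2 laboratory events needs PI and DSMC agreement and an asymptomatic, controlled event, so a treating physician cannot use it alone.

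**Conclusion.** The inconsistency is real and narrow. For irAEs without their own row, at Grade 4 or recurrent Grade 3, Table 4-4 requires a permanent stop. Table 4-7 stops only if steroids cannot be brought below 10 mg/day within 2 weeks, and Section 4.4 allows resumption on timely recovery with no exception for Table 4-4's stops.

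The documents give no rate of such events by the intravesical route, and Section 4.5.1 expects irAEs to be rare, so no frequency or number of affected patients can be claimed. It would be tempting to express the stake as remaining pembrolizumab instillations, but without an event rate such a count is only a ceiling and does not measure risk. Nor do the documents support reading this as a threat to the dose-finding result: DLT counts, the MTD and the planned analyses are unaffected.

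The conclusion rests on the protocol text alone and could be softened by the irAE guidance document. It is a minor safety-consistency correction, worth making because it costs so little.

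**What to change.** 1. In Table 4-7, split the Grade 3-4 pembrolizumab action: *Grade 4 or recurrent Grade 3: permanently discontinue. First Grade 3: withhold or discontinue according to event type, as in Table 4-4; if withheld, discontinue if prednisone equivalent is not <10 mg/day within 2 weeks.*
2. Under the Table 4-7 lead-in, add: *Table 4-4's permanent-discontinuation rules prevail over Table 4-7 and Section 4.4.*
3. In Section 4.4, in the paragraph on withholding pembrolizumab, add to the resumption sentence: *except where Table 4-4 requires permanent discontinuation.* The Grade 2 laboratory allowance needs no wording of its own, because the precedence sentence covers it.

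Check the wording against the irAE guidance document before adopting it. The cost is one table row, one sentence and one clause. Doses, visits, DLT rules and analyses do not change.
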